6. ANALYSES AND SUMMARIES

6.1. Primary Endpoint

6.1.1. Primary Endpoint/Estimand Analysis

6.1.1.1. Main Analysis

The primary endpoint is time (days) to sustained alleviation of all targeted COVID-19 signs/symptoms through Day 28 in the mITT1 population.

Sustained alleviation of all targeted COVID-19 signs/symptoms is defined as the event occurring on the first of 4 consecutive days when all symptoms scored as moderate or severe at study entry are scored as mild or absent AND all symptoms scored mild or absent at study entry are scored as absent. The first day of the 4 consecutive-day period will be considered the First Event Date.

For symptoms with no reported severity in baseline, the symptom will have to be absent in order to be counted as sustained alleviated/resolved (missing severity at baseline will be treated as mild).

Day 25 is the last possible day the symptom alleviation and resolution endpoints can be achieved (definition includes data from the subsequent three days) and Day 28 is the last day participants report their daily signs and symptoms.

The time to sustained symptom alleviation/resolution for the purpose of this study is defined as:

- For a participant with sustained symptom alleviation/resolution (event), time to event will be calculated as (First Event Date) – (First Dose Date) +1.

- For a participant that either completes Day 28 of the study or discontinues from the study before Day 28 without sustained symptom alleviation/resolution (censored), censoring date will be at the last date on which symptom alleviation/resolution is assessed, and time will be calculated as (Censoring Date) – (First Dose Date) +1 or Day 25 whichever occurs first.

The decision to require 4 consecutive days of all targeted symptoms alleviation/resolution was based on exploratory analyses of data from the ACTIV-2/A5401 study, which suggested that this choice (rather than requiring fewer consecutive days) better captured sustained symptom resolution with low probability of subsequent relapse.

Participants who are hospitalized for the treatment of COVID-19 or death from any cause during the 28-day period will be classified as not achieving sustained symptom alleviation and will be censored at Day 25.

Time to sustained alleviation of all targeted COVID-19 signs/symptoms will be summarized with Kaplan-Meier curves. Log-rank test will be used to compare the difference in time (days) to sustained alleviation of all targeted COVID-19 signs and symptoms through Day 28 between treatment groups.

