2.3. Sample Size Determination

The initial estimate of required sample size was based on the primary endpoint, the difference in time to sustained alleviation of all targeted COVID-19 associated signs/symptoms between participants who were treated ≤ 3 days after COVID-19 symptom onset with PF-07321332/ritonavir compared to placebo. The sample size is calculated based on a 2-sample test - parallel design – log-rank test, assuming a 90% power, 2-sided test at $\alpha = 0.05$, approximate accrual rate of 30 participants per day, 2 days difference in the median days to sustained alleviation of all targeted COVID-19-associated symptoms (6 days for PF-07321332/ritonavir and 8 days for placebo ie, a 25% reduction in time to sustained alleviation of all targeted COVID-19 signs/symptoms) based on the Lilly - BLAZE-1¹ and assuming a 18% study discontinuation rate, the sample size of approximately 800 participants (approximately 515 events) will provide 90% power to detect that difference.

Allowing for approximately 30% of participants with COVID-19 symptom onset > 3 days, a sample size of approximately 1140 participants will be enrolled for this study.

After the second interim analysis (80% planned enrollment through Protocol Amendment 4), in order to improve estimation precision of the treatment effect in the clinically relevant key secondary endpoint of COVID-19-related hospitalization or death from any cause, the sample size has been adjusted to approximately 1880 participants. This adjustment will provide the required total number of 26 COVID-19-related hospitalizations or death from any cause, which will have approximately 90% conditional power (based on the interim data) such that the nominal 95% CI of the treatment group difference in the event rate does not include 0 when assuming that PF-7321332/ritonavir reduces the event rate by 70% or more relative to placebo.

The sample size increase of 740 participants is based on the assumption of a 1.5% event rate for the targeted enrollment countries. The number of participants is approximately 1880 (1140 enrolled participants plus the 740 participants). Assuming a 5% premature study discontinuation rate, approximately 1980 participants will be enrolled in the study.

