An expanded definition severity of signs and symptoms that will include CRF data (hospitalization due to COVID-19 and death of any cause) is defined as follows: Participant with hospitalization due COVID-19 or death of any cause will be considered as having severe signs and symptoms, this definition overrides the observed severity of signs and symptoms from participant diary. To incorporate hospitalization and death in the severity of signs and symptoms, the date of hospitalization and date of discharged will be used. Treatment comparisons between groups for expanded severity will be presented as odds ratios with 95% CI and p-value based on logistic regression model and using the mITT1 population

This analysis will be performed for overall, baseline (Day 1), Day 2 to Day 6 (during treatment) and Day 7 to Day 28 (post treatment).

6.2.8. Time (days) to Sustained Resolution of All Targeted COVID-19 Signs/symptoms through Day 28

The secondary endpoint of time (days) from start of study intervention or placebo (Day 1) until sustained resolution of all targeted COVID-19 associated signs/symptoms will be based on self-assessment.

Sustained resolution is defined as when all targeted symptoms are scored as absent for 4 consecutive days. The first day of the 4 consecutive-day period will be considered the First Event Date.

The censoring method and analysis of time (days) to sustained resolution of all targeted COVID-19 signs/symptoms will be similar to the censoring method and analysis of the primary endpoint. The analysis will be done using mITT1 population.

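### Participants who leave without the event are, on the literal rule, kept at risk for up to three days on which no event can be dated, so median time to alleviation reads slightly too long in both arms

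*SAP*

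**What the plan says.** SAP 6.1.1.1 counts alleviation from the first day of a four-day qualifying run and draws the consequence for someone who completes the diary: "Day 25 is the last possible day the symptom alleviation and resolution endpoints can be achieved (definition includes data from the subsequent three days").

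For anyone without the event, whether a completer or an early leaver, the "censoring date will be at the last date on which symptom alleviation/resolution is assessed", and the time used is the earlier of that date and Day 25. Protocol 9.3.2 has the same rule. Neither document defines the date of assessment further.

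Three related rules matter:

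- SAP 6.1.1.1 censors participants who are hospitalised for COVID-19 or who die at Day 25. That is a separate rule and is not at issue here.
- SAP 6.1.1.2 and protocol 9.3.2.1 plan one alternative for leavers, which is to censor them at Day 25.
- SAP 6.2.8 says that the method for sustained resolution "will be similar to the censoring method and analysis of the primary endpoint".

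**The concern.** A participant whose diary stops on day d can have a recorded event no later than d-3, because a run starting on d-2 or later cannot be confirmed. If censoring is at d, that person stays in the denominator on d-2, d-1 and d and cannot contribute an event on any of them. The three-day allowance is made for completers and not for leavers.

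The effect runs one way: the daily event rate is understated and the Kaplan-Meier median is too long. The difference in medians is the primary estimand (SAP 2.1.1), so any imbalance between arms in who leaves, or when, would feed into it.

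**Working it through.** **Which date does the rule mean?** The diary ends on Day 28, so d-3 can never exceed 25. If the assessment date already meant d-3, the Day 25 cap would do nothing. The cap has work to do only if the date is the last diary day, which is why that is the literal reading.

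**Days at risk with no possible event, on that reading**

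| Last diary day d | Censored at | Last datable event | Excess days |
|---|---|---|---|
| 3 to 25 | d | d-3 | 3 |
| 26 | 25 | 23 | 2 |
| 27 | 25 | 24 | 1 |
| 28 | 25 | 25 | 0 |

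For d = 1 or 2 the excess is d days.

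**Inputs from SAP 2.3.** Medians: "6 days for PF-07321332/ritonavir and 8 days for placebo". Design: "assuming a 90% power, 2-sided test at" 0.05. Discontinuation: "assuming a 18% study discontinuation rate" in the initial sizing, and "Assuming a 5% premature study discontinuation rate" in the later one. The documents give no timing of discontinuation and no split by arm, so both are assumed below.

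**The plan's own figure.** The SAP states "approximately 800 participants (approximately 515 events) will provide 90% power to detect that difference". Freedman's formula with ratio 6/8 = 0.75 gives (1.960 + 1.282)² × (1.75/0.25)² = 10.507 × 49 = 514.9, that is 515. The event count reproduces, and it does not depend on the censoring point.

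**Mechanism.** On day t the estimated event rate equals the true rate multiplied by (at risk with d ≥ t+3) / (all counted at risk). With 18% leaving evenly over Days 1 to 27, 0.18/27 = 0.67% leave per day, so three days' worth is 2.0% of those randomised. It is a little more as a share of those still at risk. The full calculation gives an average factor of about 0.976, and 8/0.976 = 8.20 and 6/0.976 = 6.15 days.

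**Expected Kaplan-Meier medians** (exponential event times in whole days, leaving unrelated to outcome, no missed diary days)

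| Leaving | True 6 reads | True 8 reads | With d-3 |
|---|---|---|---|
| 5%, even over Days 1-27 | 6.04 | 8.05 | 6.00 / 8.00 |
| 18%, even over Days 1-27 | 6.15 | 8.20 | 6.00 / 8.00 |
| 18%, all in Days 1-7 | 6.58 | 8.57 | 6.00 / 8.00 |

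A separate simulation agreed (8.07 rather than 8.05 for the placebo median at 5%).

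**Between arms, equal leaving.** The difference in medians is 8.05 - 6.04 = 2.01, 8.20 - 6.15 = 2.05 and 8.57 - 6.58 = 1.99 days, against a true 2.00. With no drug effect and 18% leaving evenly in both arms, the rate ratio is 1.00.

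**Between arms, unequal leaving, no drug effect** (both medians 8; 2000 simulated log-rank tests; the last column is rejection in favour of the arm with fewer leavers, nominal 2.5%, Monte Carlo error roughly 0.3 to 0.6 point)

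| Leaving | Medians | Rate ratio | Rejection as written / d-3 |
|---|---|---|---|
| 18% v 9%, even, N=800 | 8.20 v 8.10 | 1.013 | 3.4% / 2.3% |
| 18% v 5%, week 1, N=800 | 8.57 v 8.15 | 1.036 | 6.0% / 2.3% |
| 18% v 5%, week 1, N=1880 | 8.57 v 8.15 | 1.036 | 8.6% / 2.5% |

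**With the true 6 v 8 effect and more leavers on active, N=800,** power is 94.8% as written against 96.4% with d-3 (18% v 9%, even), and 88.2% against 95.0% (18% v 5%, week 1).

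**The planned alternative.** Censoring leavers at Day 25 adds still more event-free time. With no drug effect it gives rate ratios of 1.08 (18% v 9%, even) and 1.29 (18% v 5%, week 1). It moves away from d-3, so it cannot serve as a check on this problem.

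**The case against.** The strongest reply is that the assessment date is undefined and that the same section explains the three-day look-ahead, so d-3 may be what the sponsor means. That reading is possible. It leaves the Day 25 cap idle, and the text would still need a definition before it could be programmed with certainty.

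The second reply is that the effect is small. This largely stands. With equal leaving the difference in medians moves by 0.05 day or less in the scenarios above. The 18% comes from the initial sizing and the later one assumes 5%. The larger distortions need 18% v 5% with every leaver gone in week 1.

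Third, SAP section 2 says that no alpha remains, so no confirmatory decision depends on this. That is right. The median difference will still be reported with nominal p-values.

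Fourth, d-3 censoring needs care. Someone with three or fewer diary days has d-3 at or below zero, and mITT1 requires only one dose, so such people can exist. Exact recovery of the true medians also assumes gap-free diaries and uninformative leaving; with missed days, the last confirmable start can be earlier than d-3. Both points stand and shape the fix.

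A reader might infer that the rule inflates only the arm with more leavers, or that it creates a false treatment difference in this trial. The documents do not support either. Both arms are inflated, and no discontinuation by arm or by day is given from which a difference could be shown.

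**Conclusion.** The point holds in limited form. On the literal reading, each leaver without the event adds up to three days at risk on which an event is impossible (two for d = 26, one for d = 27), and this lengthens the median in both arms. The inflation is about 0.04 to 0.07 day at 5% and 0.15 to 0.2 day at 18% leaving evenly, and about 0.6 day if 18% all leave in week 1. The between-arm shift is about 0.1 day, with a rate ratio near 1.01, at 18% v 9% spread evenly. It becomes material only with early and clearly unequal leaving.

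The direction follows from the rule itself. The sizes rest on assumed timing and split of leaving, roughly exponential event times and complete diaries. The estimate and nominal p-values are affected. The 515-event calculation is not. The same rule carries over to sustained resolution. The change is worth making because the bias is systematic, no planned analysis removes it, and the correction is short.

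**What to change.** In SAP 6.1.1.1 and protocol 9.3.2:

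- Censor participants without the event at the last day on which a four-day run could have started and been confirmed, that is, last diary day minus 3, with a maximum of Day 25.
- Give zero time to those with three or fewer diary days, and report their number by arm.
- Leave the Day 25 rule for hospitalisation and death unchanged.
- Keep Day 25 censoring of leavers only as the labelled sensitivity analysis in SAP 6.1.1.2.
- Apply the same change to sustained resolution in SAP 6.2.8.

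**Cost.** One or two sentences in each document and a line of derivation code, with no new data. Medians become slightly shorter in both arms. Very early leavers contribute no risk time. If leaving is even over Days 1 to 27, that is 0.18 × 3/27 = 2.0%, about 40 of 1980, at 18%, and 0.05 × 3/27 = 0.56%, about 11, at 5%. It would be 0.18 × 3/7 = 7.7%, about 153, if 18% all left evenly within week 1. Because this alters the primary analysis after three interim analyses, it has to be recorded in an amendment, as protocol section 9 requires for major changes to that analysis.

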 6. Known medical history of active liver disease (other than nonalcoholic hepatic steatosis), including chronic or active hepatitis B or C infection, primary biliary cirrhosis, Child-Pugh Class B or C or acute liver failure.
 7. Receiving dialysis or have known renal impairment.
 8. Known HIV infection with viral load > 400 copies/mL or taking prohibited medications for HIV treatment (from known medical history within past 6 months of the screening visit) (Appendix 8).
 9. Suspected or confirmed concurrent active systemic infection other than COVID-19 that may interfere with the evaluation of response to the study intervention.
 10. Any comorbidity requiring hospitalization and/or surgery within 7 days prior to study entry, or that is considered life threatening within 30 days prior to study entry, as determined by the investigator.
 11. History of hypersensitivity or other contraindication to any of the components of the study intervention, as determined by the investigator.
 12. Other medical or psychiatric condition including recent (within the past year) or active suicidal ideation/behavior or laboratory abnormality that may increase the risk of study participation or, in the investigator’s judgment, make the participant inappropriate for the study.

Prior/Concomitant Therapy:

13. Current or expected use of any medications or substances that are highly dependent on CYP3A4 for clearance and for which elevated plasma concentrations may be associated

with serious and/or life-threatening events during treatment and for 4 days after the last dose of PF-07321332/ritonavir (see [Appendix 8](#)).

14. Concomitant use of any medications or substances that are strong inducers of CYP3A4 are prohibited within 28 days prior to first dose of PF-07321332/ritonavir and during study treatment (see [Appendix 8](#)).
15. Has received or is expected to receive monoclonal antibody treatment, antiviral treatment (eg, molnupiravir), or convalescent COVID-19 plasma.
16. Has received any SARS-CoV-2 vaccination within 12 months of screening.

Note: Participants entering the study must not receive any dose of a SARS-CoV-2 vaccine prior to Day 34.

Prior/Concurrent Clinical Study Experience:

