9.3.1. General Considerations

Descriptive statistics for all efficacy endpoints by treatment group and visit will be provided.

The number of participants screened will be reported. The number of participants randomized to the double-blind treatment phase, completing the study drug administration, completing the study, and discontinued the study will be summarized from the FAS analysis set for each treatment group.

Baseline demographic and other characteristics will be tabulated for the FAS analysis set and summarized by treatment group. Quantitative variables will be described by standard descriptive statistics (mean, standard deviation, minimum, and maximum), and qualitative variables will be summarized by frequency tables with number and proportion in each category (with the corresponding sample sizes).

For continuous endpoints, MMRM analysis of covariance model will be used to analyze change from baseline over time. Estimated mean differences between treatments and their respective 95% CI and p-values will be calculated.

Binary endpoints will be summarized with the number and percent of participants satisfying the endpoint. Comparisons between groups will be presented as odds ratios with 95% confidence intervals based on logistic regression analysis with terms for treatment.

For categorical endpoints, proportion of participant for each category will be summarized for each group.

For count endpoints, the total number of the events and average number of events will be summarized for each group.

Time-to-event endpoints will be summarized with Kaplan-Meier curves. Log-rank test will be used to compare the median time-to-event between the treatment group. Rate ratios or hazard ratios and the associated 95% 2-sided CIs will be estimated by Cox proportional hazards models, including treatment and the strata as covariate.

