3.5. Stratification Variables

Randomization was stratified by geographic region, by vaccination status and by COVID-19 symptom onset (≤ 3 days vs >3 to 5 days).

Vaccination status is defined as completely vaccinated (high risk) and not vaccinated (standard risk).

Geographical region is defined as follows:

- US region: country of the United States, including Puerto Rico.
- Europe region: countries of Bulgaria, Czech Republic, Hungary, Poland, Spain, Ukraine, Slovakia and Romania.
- Rest of the World region: countries of Argentina, Brazil, Colombia, Japan, Malaysia, Mexico, South Africa, Republic of Korea, Taiwan, Thailand, and Turkey.

Baseline and stratification variables defined above will be applied to the analyses depending on the analysis population used:

- mITT1 analysis will include: Baseline viral load, baseline serology status, geographic region, vaccination status and symptom onset days to first dose date (≤ 3 days, >3 days). Detail will be described in each endpoint if applied.

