5.2. General Methods

All data will be presented by treatment groups. Descriptive statistics will be provided for efficacy endpoints. The following listing of individual participants data will also be produced: (Disposition Events, Potentially Important Protocol Deviations, Subject Evaluation Groups, Demographic Information, Primary Diagnosis, Concomitant Medications, Compliance with Study Intervention, primary efficacy endpoint [time to sustained alleviation of all targeted signs and symptoms through Day 28], and the two key secondary endpoints [proportion of participants with COVID-19-related hospitalization or death from any cause through Day 28; number of COVID-19-related medical visits through Day 28], Adverse Events, Laboratory Data – Standardized (all the variables that are listed in the SAP [Section 6.4](#) plus visit ID, participant ID, treatment).

The number of participants screened will be reported. The number of participants randomized to the double-blind treatment phase, completing the study drug administration, completing the study, completing the follow-up phase (through Day 34 visit) and discontinued the study will be summarized from the FAS analysis set for each treatment group.

Baseline demographic and other characteristics will be tabulated for the FAS and summarized by treatment group. Quantitative variables will be described by standard descriptive statistics (mean, standard deviation, median minimum, and maximum), and qualitative variables will be summarized by frequency tables with number and proportion in each category (with the corresponding sample sizes).

For mITT1 population, strata will be region, vaccination subgroup/strata, onset of signs and symptoms of COVID-19 (≤ 3 days, $>3-5$ days), nasopharyngeal (Y/N), and baseline viral load.

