6.1.1.2. Sensitivity and Supplemental Analyses

Sensitivity analyses will be performed to the primary efficacy endpoint:

The primary efficacy analyses will also be conducted using the PP population as supplemental analyses.

The primary endpoint will also be analyzed in which participants who discontinued the study before Day 28 without event will be censored at Day 25.

For sensitivity analysis of primary endpoint, Cox proportion hazard models with terms including treatment and treatment strata (ie, region, vaccination, baseline serology, baseline viral load $<10^4$ copies/mL vs $\geq 10^4$ copies/mL). These factors will be used to estimate the hazard ratio (the ratio of alleviation of all targeted signs and symptoms) and its 95% CI. Additional analyses may be performed adjusting for baseline covariates (such as age, gender, etc) as additive terms to the primary model, if necessary.

Based on FDA request, a sensitivity analysis excluding participants only from Site 1488 will be conducted as well.

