6.4. Subset Analyses

Subgroup analyses of the primary endpoint and key secondary endpoint (hospitalization due to COVID-19 and death of any cause) will only be performed for vaccination status and others will be analyzed if necessary for post hoc. The subgroup variables include:

- Age group (<65, ≥ 65);
- Sex;
- Race;
- Vaccination status. The vaccination subgroup is defined as follows:
 - a) Participant who enrolled prior to PA #5 and were completely vaccinated are considered high risk group.
 - b) Participants who enrolled prior to PA#5 and were not vaccinated, plus all participants enrolled after implementation of PA#5 are considered as standard risk group.
- Baseline serology (PCR positive, PCR negative);
- Baseline viral load defined as: <10⁴ copies/mL vs ≥10⁴ copies/mL;
- Maximum severity of targeted baseline signs and symptoms (mild, moderate, severe)
- Vaccination status and by maximum severity of targeted baseline signs and symptoms (mild, moderate, severe)
- Baseline viral load defined as: <10⁷ copies/mL vs ≥10⁷ copies/mL;
- BMI category (<30, ≥30);
- Type of COVID-19 variant (i.e., Omicron, BA2);
- Baseline Comorbidities:
 - Smoking;

- Chronic lung disease requiring medication;
- Hypertension (taking medications for hypertension);
- Cardiovascular disorders;
- Diabetes (taking medications for diabetes) for safety reporting;
- Chronic kidney disease;
- Sickle cell disease;
- Neurodevelopmental disorders;
- Cancer other than localized skin cancer;
- Medical-related technological dependence.

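### The supporting Cox model for the primary endpoint (SAP 6.1.1.2) omits symptom onset, a randomisation factor, and does not say which definition of vaccination it uses

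*SAP*

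**What the plan says.** Protocol 4.1 and SAP 2.2 and 3.5 give three randomisation factors: region, vaccination status, and symptom onset (up to 3 days, or more than 3 to 5 days).

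For the primary test, SAP 6.1.1.1 states: "Log-rank test will be used to compare the difference in time (days) to sustained alleviation of all targeted COVID-19 signs and symptoms". SAP Appendix 1 and Protocol 9.3.2 also name no strata.

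For the supporting Cox model, SAP 6.1.1.2 gives the terms as "treatment and treatment strata (ie, region, vaccination, baseline serology, baseline viral load", with viral load split at 10^4 copies/mL. In SAP 5.2, the general rule begins "For mITT1 population, strata will be region, vaccination subgroup/strata, onset of signs and symptoms of COVID-19" and continues with nasopharyngeal sampling and baseline viral load. SAP 3.5 also lists onset for mITT1 analyses, but adds "Detail will be described in each endpoint if applied". Protocol 9.3.1 says hazard ratios are "estimated by Cox proportional hazards models, including treatment and the strata as covariate". Protocol 9.3.2.1 refers to treatment strata without defining them.

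On vaccination, SAP 3.5 says "Vaccination status is defined as completely vaccinated (high risk) and not vaccinated (standard risk". SAP 6.4 says that "all participants enrolled after implementation of PA#5 are considered as standard risk group". Exclusion 16 in Protocol 5.2 reads "Has received any SARS-CoV-2 vaccination within 12 months of screening".

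**The concern.** A model presented as adjusting for the strata would be expected to contain the factors used to randomise. This one drops one of the three and adds two baseline measurements that were not used to randomise. SAP 6.1.1.2 gives no reason, and its list conflicts with SAP 5.2. Two programmers working from the same SAP could fit different models.

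This matters because the log-rank test gives no effect size. The hazard ratio from this Cox model is the only primary-endpoint estimate in SAP 6.1.1 with a specified confidence interval. SAP Appendix 1 uses a Cox model in three rows: the sensitivity analysis, the analysis without Site 1488, and the analysis by vaccination status. The undefined vaccination term adds a second source of divergence.

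**Working it through.** **1. The factor lists side by side.**

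| Factor | Randomisation | SAP 5.2 (mITT1) | SAP 3.5 (mITT1, if applied) | SAP 6.1.1.2 Cox |
|---|---|---|---|---|
| Region | yes | yes | yes | yes |
| Vaccination | yes | yes | yes | yes |
| Symptom onset | yes | yes | yes | **no** |
| Baseline serology | no | no | yes | yes |
| Baseline viral load | no | yes | yes | yes |
| Nasopharyngeal sample | no | yes | no | no |

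SAP 3.5 leaves the choice to each endpoint, so it is not contradicted. SAP 5.2 carries no such qualifier.

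**2. Does onset vary in the primary set?** In mITT (treated within 3 days) it cannot. In mITT1 it can: Protocol 9.5 allows for about 30% with onset more than 3 days earlier.

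**3. The plan's own event count.** Freedman's formula for a log-rank test without strata, with 90% power, two-sided 0.05 and median ratio 6/8 = 0.75:

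events = (1.960 + 1.2816)² × [(1 + 0.75)/(1 − 0.75)]² = 10.508 × 49 = 515.

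This matches the stated figure, so the planned power was for an unstratified test.

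**4. What stratification is worth (simulation).**

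- From the documents: onset more than 3 days 30%, placebo median 8 days, last possible event Day 25, discontinuation 18% at n = 1140 and 5% at n = 1980. The vaccinated share is 60% at n = 1140 (Amendment 4 rationale, Protocol Appendix 11), hence 0.6 × 1140/1980 = 34.5% at n = 1980.
- Assumed: region shares 50/30/20, permuted blocks of 4, exponential times rounded up to days, and every stratum hazard ratio. The documents give no stratum effects.

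Stratum hazard ratios are listed as region step/vaccination/onset. Power is at a treatment hazard ratio of 1.15, where above 1 means faster alleviation.

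| Stratum effects | n | Type I error, unstratified | Power, unstratified | Stratified by region + vaccination | Stratified by all three | Gain from onset |
|---|---|---|---|---|---|---|
| 1.4/1.4/1.3 | 1140 | 4.0% | 52.2% | 56.7% | 57.1% | 0.4 |
| 1.5/2.0/1.5 | 1140 | 3.3% | 44.4% | 54.3% | 55.5% | 1.2 |
| 1.4/1.4/1.3 | 1980 | 4.1% | 78.1% | 81.7% | 82.0% | 0.3 |
| 1.5/2.0/1.5 | 1980 | 3.4% | 71.5% | 79.5% | 80.6% | 1.1 |

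Share of the gap recovered by region and vaccination alone: 4.5/4.9 = 92%, 9.9/11.1 = 89%, 3.6/3.9 = 92%, 8.0/9.1 = 88%.

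With no stratum effects, type I error is 5.0% (n = 1140) and 5.1% (n = 1980). With 1.2 for each factor it is 4.8% and 4.6%, and full stratification gains 1.0 point (57.0% to 58.0%; 81.3% to 82.3%). At the planned effect (medians 6 v 8 days) the gap between unstratified and fully stratified tests is at most 99.3% − 97.9% = 1.4 points at n = 1140, and none at n = 1980.

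Monte Carlo error on power is about 0.5 points near 50%, so the smaller onset gains are of the same order. A repeat run at n = 1980 gave onset gains of 83.1 − 82.8 = 0.3 and 81.8 − 80.4 = 1.4, and unstratified type I error of 4.1% and 2.6%. With onset the only prognostic factor (n = 1140, treatment hazard ratio 1.2, region 40/30/30, half vaccinated), unstratified v fully stratified power was 79% v 79% for an onset hazard ratio of 1.5, and 76% v 79% for 2.0.

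These are stratified log-rank results standing in for the Cox model, which was not itself simulated.

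**5. The vaccination term.** Take a participant enrolled after Amendment 5 and completely vaccinated more than 12 months before screening. Exclusion 16 does not bar this person. SAP 3.5 makes the participant high risk; SAP 6.4 makes the same participant standard risk. Planned enrolment after Amendment 5 is 1980 − 1140 = 840. If 10%, 30% or 50% of these were such participants, 84, 252 or 420 would be classified differently (4%, 13% or 21% of 1980). The shares are pure assumption.

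**The case against.** The other side has a good case on size. The primary log-rank is valid, consistently specified, and matches the 515-event calculation. Its p-value is only nominal, because no alpha remained after the first interim analysis, so no decision rule depends on it. Region and vaccination are already in the Cox model and recover about nine tenths of the gap. SAP 3.5 lets each endpoint choose its variables, and SAP 5.2.2 uses the same four-factor list, without onset, for continuous endpoints. Protocol 9.3.2.1 and SAP 6.1.1.2 also allow further covariate-adjusted models. SAP 6.4 is a subgroup definition, and it is coherent as a risk grouping because exclusion 1 now bars the listed risk factors.

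Most of this stands, and it rules out two stronger readings that a reader might infer. The first is that the unstratified test is wrong or inflates type I error. The documents do not support this: the test is at most conservative, and only if the strata are prognostic. The second is that power gaps of 4 to 11 points are the price of this omission. Those gaps compare no stratification with full stratification under assumed effects, and onset accounts for only a small part of them.

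The objection does not remove the mismatch. SAP 5.2.2 covers continuous endpoints, not this model, and SAP 5.2 names onset for mITT1 without qualification. The extra covariate models are optional. Nothing in SAP 6.1.1.2 says which meaning of vaccination applies.

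**Conclusion.** The point holds as a specification defect with a modest statistical effect. The list in SAP 6.1.1.2 conflicts with SAP 5.2 and with the plain sense of Protocol 9.3.1, and it leaves out a randomisation factor that varies in the primary set. The vaccination term has two definitions that disagree for participants whom the current criteria admit; the documents do not show how many there are.

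Adding onset is worth about 0.3 to 1.2 power points at a hazard ratio of 1.15 under the two strong scenarios, and about 3 points if onset alone had an assumed hazard ratio of 2.0. All these figures rest on assumed stratum effects. The reason to act is to have one unambiguous model behind the only interval estimate specified for the primary endpoint. It should be corrected, but it does not threaten the validity of the primary test.

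**What to change.** In SAP 6.1.1.2, fit the Cox model with treatment and all three randomisation factors by adding symptom onset (up to 3 days v more than 3 days). Label baseline serology and baseline viral load as additional covariates, not strata. State that the vaccination term is the randomisation stratum, and keep the SAP 6.4 risk grouping for the subgroup analysis. Align SAP 5.2 and the Cox rows of Appendix 1 with this list. The cost is SAP wording and one model term.

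Keep the unstratified log-rank as the primary test. Optionally, report a log-rank stratified by the three factors as a supporting analysis, with a numerical rule for collapsing sparse cells fixed before the final unblinding. Its cost is a second nominal p-value for the primary endpoint, which must be disclosed as added after the interim analyses. If the strata are not prognostic, it loses under 1 point of power at a hazard ratio of 1.15 (58.3 − 57.6 = 0.7 at n = 1140; 83.7 − 83.5 = 0.2 at n = 1980).
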